## 3.6 THERAPY ADMINISTRATION

### 3.6.1 Dabrafenib and trametinib administration

- Dabrafenib and trametinib will be provided by the Supporting Company, Novartis free of charge and will be disposed of per Institutional Guidelines
- Dabrafenib and trametinib should be taken as follows:  
Dabrafenib will be administered orally twice daily (BID) for Days 1-28 of a 28-day cycle.
- Trametinib will be administered orally once daily (QD) for Days 1-28 of a 28-day cycle.
- Subjects should be instructed to take the dabrafenib and trametinib concurrently in the morning, at approximately the same time every day. The second (evening) dose of dabrafenib (150 mg) should be administered approximately 12 ( $\pm$  4) hours apart from the first dose (morning) of dabrafenib.
- Subjects should be instructed to swallow whole capsules of dabrafenib and not chew or open them.
- If a subject vomits after taking study drug, the subject should be instructed not to retake the dose and wait for the next scheduled dose. The occurrence and frequency of any vomiting during a treatment cycle must be noted
- If a subject misses a dose, he/she should be instructed not to double the next regularly scheduled dose. However, subject may take the missed dose immediately if the next scheduled dose is at least 6 hours later for dabrafenib and 12 hours later for trametinib. Subject may then take the next dose at the scheduled time.
- Subjects must avoid consumption of grapefruit, grapefruit hybrids, pomelos, star-fruit, Seville oranges or products containing the juice

of each during the entire study and preferably 7 days before the first dose of study medications, due to potential CYP3A4 interaction with the study medications.

- Orange juice is allowed.
- No herbal or dietary supplements are permitted.
- Multivitamins are permitted.

### **3.6.2 SpartaLizumab administration in adjuvant setting for non pCR patients**

Spartalizumab (100mg liquid in vial for infusion solution) will be administered as a flat dose of 400mg intravenously over at least 30 minutes every 28 days in the adjuvant setting along with dabrafenib and trametinib in patients who have not achieved a pCR. Infusion can be up to 2 hours if clinically indicated. Subjects should not receive pre-medication to prevent infusion reaction before the first infusion of study treatment. If a subject experiences an infusion reaction, he/she may receive pre- medication on subsequent dosing days. The pre-medication should be chosen per institutional standard of care, at the discretion of the investigator. SpartaLizumab will be provided by Novartis free of charge and will be disposed of per Institutional Guidelines.

Acute allergic reactions should be treated as needed per institutional standard of care. In the event of anaphylactic/anaphylactoid reactions, this includes any therapy necessary to restore normal cardiopulmonary status. If a subject experiences a Grade 3 anaphylactic/anaphylactoid reaction, the subject will be discontinued from the study.

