#### Prior Experience with Investigational Agents

The COMBI-I study is a multicenter trial exploring the safety and efficacy of dabrafenib, trametinib and spartalizumab in patients with BRAF V600 mutated unresectable or metastatic melanoma. In Part 1 of the trial (safety run-in cohort), standard dosing of dabrafenib (150mg orally twice daily), trametinib (2mg daily) and spartalizumab (400mg IV every 4 weeks) was utilized. A total of 9 patients were enrolled and there was no excessive toxicity seen and this dosing was utilized in Part 2 which was designed to be a biomarker exploration cohort. An additional 27 patients were treated on Part 2 for a total of 36 evaluable patients for safety and efficacy. At the time of data analysis, the median follow up time was 19.9 months (16.5-25.1 months range) and treatment was ongoing for 13 patients. All patients had some form of adverse event, with 78% having experienced a grade 3 toxicity. The most common grade 3 toxicities were pyrexia (17%) and pruritus (11%). Grade 3 laboratory evaluations were noted including elevated creatinine phosphokinase (8%), amylase (8%) and gamma-glutamyltransferase (8%) levels, in keeping with prior studies. All patients required dose adjustment/interruption to mitigate toxicities and 17% of patients had toxicities leading to cessation of the triplet therapy. In terms of efficacy, the overall response rate was 78% with 42% achieving confirmed complete response, which included 20% with elevated LDH at baseline and 40% with stage IV M1c disease. The median PFS was 23.7 months, including 10.7 months for higher risk patients with elevated LDH values at time of enrollment. The median duration of response was 20.7 months with 29% of responders experiencing subsequent progression. The median overall survival was not reached in this cohort. Part 3 of this trial which is a global, placebo-controlled randomized trial of dabrafenib, trametinib and placebo vs. dabrafenib, trametinib and spartalizumab is currently in enrollment.

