### 3.3.2 Dose Modification

#### ***Dose Modification of Dabrafenib and Trametinib and Spartalizumab for General Toxicities Related to Study Drug(s)***

In the event of a clinically significant grade 3 or 4 hematologic or non-hematologic AE, treatment may be withheld and supportive therapy administered as clinically indicated. If the toxicity or event resolves to baseline or Grade 1 in less than or equal to 21 days of stopping therapy, treatment may be restarted. Dose reduction should be considered as clinically indicated at the discretion of the treating oncologist. Any dose adjustment or interruption will be recorded.

If the toxicity does not resolve to at least Grade 1 in less than or equal to 21 days, withdrawal from the trial is recommended. However, if the investigator agrees that further treatment will benefit the subject, treatment can continue with a reduction of one or both study drugs.

Suggested dose reduction of each drug is as follows in Table 4. These dose reductions of dabrafenib and trametinib do not need to be made concurrently and will be up to the discretion of the treating investigator.

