**Table 5 Dose Modification Guidelines – General**

CTCAE Grade	Action and Dose Modification
Grade 1 or Grade 2 (tolerable)	Continue study treatments at same dose level (no dose modification)
Grade 2 (Intolerable)	
1 st or 2 nd occurrence	Interrupt study treatments until toxicity resolves to $\leq$ grade 1 then restart at same dose level
3 rd or occurrence	Interrupt study treatments until toxicity resolves to $\leq$ grade 1 then restart at next lower dose level
4 th or greater occurrence	Interrupt study treatments until toxicity resolves to $\leq$ grade 1 then restart at two dose levels lower than the starting dose or discontinue treatments per investigator discretion
Grade 3	
1 st occurrence	Interrupt study treatments until toxicity resolves to $\leq$ grade 1 or baseline then restart at next lower dose level
2 nd occurrence	Interrupt study treatments until toxicity resolves to $\leq$ grade 1 or baseline then restart at two dose levels lower than the starting dose
3 rd occurrence	Discontinue treatments.
Grade 4	
1 st occurrence	Discontinue treatments

For dabrafenib and/or trametinib related adverse events: if following an interruption of dabrafenib and trametinib, an AE doesn't recover to  $\leq$  Grade 1 or baseline within 4 weeks, dabrafenib and trametinib must be discontinued.

No dose reductions are allowed for spartalizumab. Dose interruption for spartalizumab includes delaying or withholding the treatment for any reason as well as an interruption of treatment during an infusion. All dose interruptions and the reason for the dose interruption must be recorded. Dose interruption for spartalizumab includes delaying or withholding the treatment for any reason as well as an interruption of treatment during an infusion. Subjects with adverse events suspected to be related to spartalizumab including those of potential immune-mediated etiology (irAE) must be permanently discontinued from spartalizumab if (1) the AE doesn't recover to  $\leq$  Grade 1 or baseline within 12 weeks and/or (2) the dose of steroids (for the management of irAE) remains  $> 10$  mg/day prednisone or equivalent for  $> 12$  weeks. The 12 week timeframe will begin from the time the irAE reaches a grade that leads to spartalizumab interruption.

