**Table 12 Adjuvant Time and Event Table for Pathologic Non-Responders (spartalizumab, dabrafenib and trametinib)**

	Post Operat iv eh	Week 12 i	Week 16 i	Week 20 i	Week 24 i	Week 28 i	Week 32 i	Week 36 i	Week 40 i	Week 44 i	Week 48 i	Week 52 i	EOT j
Concurrent medications	X	X	X	X	X	X	X	X	X	X	X	X	X
AEs	X	X	X	X	X	X	X	X	X	X	X	X	X
PE/Vitals/ECO Ga		X	X	X	X	X	X	X	X	X	X	X	X
CBC with diff		X	X	X	X	X	X	X	X	X	X	X	X
Serum chemistry b		X	X	X	X	X	X	X	X	X	X	X	X
TSH, fT4				X			X			X			
Echocardiogram c		X			X			X			X		
12-lead EKG		X			X			X			X		X
Research Biopsy d													
If evidence of disease recurrence or metastasis													
Research Blood e		X			X			X			X		X
Research microbiome collection f		X						X					X

Disease Assessment g				X			X			X			X
Spartalizumab		X	X	X	X	X	X	X	X	X	X		
Dabrafenib and trametinib dosing	X	Continuous Daily Dosing											

- a. Includes systolic and diastolic blood pressure, pulse rate, temperature and weight.
- b. Albumin, alkaline phosphatase, total bilirubin, bicarbonate, BUN, calcium, chloride, creatinine, glucose, LDH, magnesium, phosphorus, potassium, total protein, AST, ALT, sodium.
- c. Repeat echocardiogram will be performed at month 3 and 6 and at the discretion of the investigator if there are symptoms concerning for heart failure.
- d. Should a biopsy be performed as part of standard practice, this study may request up to 4 additional cores for correlative studies.
- e. 50ml of blood will be obtained at each time point for correlative correlates.
- f. Microbiome will be collected at week 12, 36 and at recurrence. OMNIgene kits, or equivalent, will be provided
- g. PET/CT or CT of the chest, abdomen, pelvis (neck if clinically indicated) and brain MRI (or CT of the head with contrast if MRI is contraindicated).
- h. Dabrafenib and trametinib combination therapy will resume approximately two days after the patient is able to resume normal oral intake and ideally should be within 2 weeks of date of surgery. This visit could be a telephone assessment by research nurse
- i. These time points are +/- 7 days.
- j. End of treatment is defined as completion of 44 weeks of adjuvant dabrafenib/trametinib, experiencing SAE or intolerable AE mandating discontinuation of treatment or the development of progressive disease

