### **Statistical Analyses**

For the primary objective, separately by group (patients who do/do not achieve a pCR at 8 weeks), the 12-month RFS rate will be estimated with a 95% confidence interval by using the Kaplan-Meier method. RFS is defined from time of surgery to any recurrence event (local or distant disease development or death due to melanoma. In addition, in patients who do not achieve a pCR, the 12-month RFS rate will be compared with the historical rate of 50% by using a two-sided exponential MLE test. Cox proportional hazards regression models will be fit to assess the association between various clinical, demographic, and disease covariates and RFS separately by pathologic response group.

For safety, the rate of grade 3+ adverse events will be tabulated and presented by group. For overall survival (OS) and distant metastasis-free survival (DMFS), 12-month rates will be reported with 95% confidence intervals, and Cox regression models will be used to assess the association between similar covariates as above and both OS and DMFS separately by group. OS is defined as time from treatment initiation to death. DMFS is defined as time from treatment initiation to development of documented distant metastatic disease outside the loco-regional site of the primary tumor or lymph node metastasis.

For the exploratory objectives, immunological and molecular features will be assessed quantitatively at baseline and at surgical resection. Kruskal-Wallis tests will be used to compare these parameters at each time point between responders (pCR) and non-responders (no pCR). Changes in each parameter from baseline to surgery will also be compared between responders and non-responders. Circulating tumor markers will be assessed at baseline and several on-study time points. Markers and changes in markers over time will be compared between responders and non-responders by using Kruskal-Wallis tests. In addition, generalized linear mixed models may be used to model these markers over time.

Finally, to assess the impact of neoadjuvant therapy on surgical resectability, a survey will be provided to surgeons regarding the difficulty of surgery (Appendix D). These data will be subjective and will be summarized graphically as numbers permit.

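### Two toxicity rules take patients out of the study rather than off drug, and no follow-up or censoring rule for RFS covers them

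*Combined protocol and SAP*

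**What the plan says.** Two rules use off-study wording. Section 3.6.2, on spartalizumab infusion, is mandatory: "If a subject experiences a Grade 3 anaphylactic/anaphylactoid reaction, the subject will be discontinued from the study". Section 3.3.2, on general toxicities, is advisory. If toxicity has not resolved to Grade 1 within 21 days, "withdrawal from the trial is recommended", but "if the investigator agrees that further treatment will benefit the subject, treatment can continue with a reduction of one or both study drugs".

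Other toxicity rules stop drug and say nothing about leaving. In the text under Table 5, an unresolved event attributed to the oral drugs leads to this: "within 4 weeks, dabrafenib and trametinib must be discontinued". For spartalizumab, patients "must be permanently discontinued from spartalizumab if (1) the AE doesn't recover" within 12 weeks. Tables 7, 8 and 9 (visual changes, LVEF, QTc) also speak of discontinuing drug. Footnote j of Table 12 defines end of treatment to include "experiencing SAE or intolerable AE mandating discontinuation of treatment or the development of progressive disease", and the table has no column after that visit.

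The endpoint is given in Section 7.0, Statistical Analyses: "RFS is defined from time of surgery to any recurrence event (local or distant disease development or death due to melanoma". The 12-month rate is a Kaplan-Meier estimate, and in non-pCR patients it is compared with 50% by an exponential test. No censoring rule is stated. Sample Size and Power assumes two further years of follow-up after accrual, and Section 2.2 promises recurrence patterns, DMFS and OS in all treated patients.

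**The concern.** A patient who is off drug can still be scanned and contacted. A patient who is off study, with nothing in the plan to the contrary, presumably cannot. Under the two off-study rules such patients would contribute no later RFS, DMFS or OS data and would be censored when they leave. Kaplan-Meier and exponential methods assume that censored patients have the same later relapse risk as those still followed. Patients who leave because of toxicity may not.

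The primary analysis is a single arm of about 24 patients against a fixed historical rate, so there is no control arm in which the same loss could offset. Outcomes that were never collected cannot be recovered at analysis. Sites could also differ, because Section 3.3.2 and the text under Table 5 give different time limits and different consequences for overlapping situations.

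**Working it through.** **The rules side by side**

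| Place | Trigger | Consequence |
|---|---|---|
| Section 3.6.2 | Grade 3 anaphylactic/anaphylactoid reaction | off study, mandatory |
| Section 3.3.2 | not resolved to Grade 1 in 21 days | off trial, recommended; investigator may continue treatment at reduced dose |
| Text under Table 5, oral drugs | no recovery in 4 weeks | off both oral drugs, mandatory |
| Text under Table 5, spartalizumab | no recovery, or steroids above the stated level, at 12 weeks | off spartalizumab, mandatory |
| Tables 7, 8, 9; Table 12 footnote j | specific events; SAE or intolerable AE | off drug / end of treatment |

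The second row conflicts with the third and fourth on timing, on what the patient leaves, and on whether the investigator has discretion.

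**Inputs**
- 24 non-pCR patients, null 50%, target 75% (Sample Size and Power). The plan's enrolment step reproduces: 24 / 0.60 = 40. The 80% power figure depends on a variance convention that the plan does not state; nothing below uses it.
- 17%: Section 3.3.1 reports that "17% of patients had toxicities leading to cessation of the triplet therapy". This is cessation of drug in 36 patients with unresectable or metastatic disease. Using it as the share leaving the study is an assumption, towards the upper end. 0.17 × 24 = 4.08, about 4 patients.
- Assumptions without a source in the documents: exit uniform over months 0 to 6, and leavers' relapse hazard r times that of the others.

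**Scenario A: leavers' hazard is r·h throughout, true 12-month RFS fixed at 50%.** Time t is in years. h solves 0.83·exp(−h) + 0.17·exp(−r·h) = 0.50. The share of leavers still in the study is G(t) = 1 − 2t up to t = 0.5, then 0. The Kaplan-Meier limit is exp(−∫λ(t)dt) over one year, with

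λ(t) = h·[0.83e^(−ht) + 0.17·r·G(t)·e^(−rht)] / [0.83e^(−ht) + 0.17·G(t)·e^(−rht)].

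| r | h | Kaplan-Meier at 12 months | bias (points) |
|---|---|---|---|
| 0.5 | 0.770 | 47.2% | −2.8 |
| 1 | 0.693 | 50.0% | 0 |
| 1.5 | 0.645 | 51.7% | +1.7 |
| 2 | 0.612 | 52.9% | +2.9 |
| 3 | 0.570 | 54.1% | +4.1 |

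**Scenario B: hazard changes only at exit.** The observed hazard is then h throughout, so Kaplan-Meier tends to exp(−h), while

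true RFS = 0.83·e^(−h) + 0.17·e^(−rh)·(e^k − 1)/k, with k = (r − 1)·h·T and T the exit window in years.

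With true RFS 50%, r = 1.5 to 3 gives 51.9% to 55.5% for T = 6 months and 51.5% to 54.5% for T = 44 weeks.

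Worked example at the target: e^(−h) = 0.75, h = 0.2877, T = 44/52 = 0.846, r = 2. Then k = 0.2434, leavers' RFS = 0.5625 × 1.1323 = 0.637, and true RFS = 0.83 × 0.75 + 0.17 × 0.637 = 73.1%, against a Kaplan-Meier value of 75.0%. At r = 3 the true value is 71.5%; at r = 0.5 it is 76.1%, and the bias reverses.

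**Bounds that need no hazard assumption.** Suppose 4 of 24 leave at the start and 5 of the other 20 relapse by 12 months. Kaplan-Meier gives 15/20 = 75.0%. If all 4 relapse the rate is 15/24 = 62.5%; if none do, 19/24 = 79.2%. The span is 4/24 = 16.7 points.

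**The case against.** A reader might infer that the protocol removes patients from the trial for persistent toxicity as a matter of course, and that RFS would therefore be overstated in about 17% of the set. The documents do not support that:

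- Section 3.3.2 only recommends withdrawal and allows the investigator to continue. It also applies before surgery, when a patient is not yet in the non-pCR RFS set.
- Section 3.6.2 covers Grade 3 reactions only, and no frequency is given.
- Most toxicity stops fall under rules that stop drug only. The 17% is itself a drug-cessation figure from another setting, with no six-month timing.
- Censoring is inferred from silence. The assumed follow-up and the commitment to DMFS and OS in all treated patients suggest that follow-up was intended, and the wording may simply be loose.
- The direction is unknown. The documents give no relapse risk after stopping for toxicity, and Section 1.3 reports 5 of 8 relapses in earlier non-pCR patients while still on dabrafenib and trametinib.
- Even at 3 times the hazard, the bias in Scenario A is 4.1 points against a 25-point target difference.

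All of this stands as a limit on size and direction. It does not remove the defect. The protocol uses off-drug wording where it means off drug, and Section 3.0 uses removal from the study literally, for unresectable patients who are replaced. A sample-size assumption is not a follow-up procedure. The lack of assessments after end of treatment affects everyone, so these two rules do not create that gap, but it leaves nothing to offset them.

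**Conclusion.** The point holds as a conflict in wording plus a missing rule. Two toxicity rules take or recommend taking patients out of the study, others for overlapping situations stop drug only, and nothing keeps those who leave in RFS, DMFS or OS follow-up. The loss could make censoring of the primary endpoint informative. That it would do so, or would favour the regimen, is not established.

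Under the assumed 17% exit in months 0 to 6 with true RFS 50%, Scenario A gives no bias at equal hazard, about +2 to +4 points at 1.5 to 3 times the hazard, and a negative bias at lower hazard. If the hazard rises only at exit, the top of that range becomes +5.5. Since not every toxicity stop is a study exit, this is an upper-end illustration and not a forecast. The firmer figure is that each unknown outcome moves 12-month RFS by up to 1/24, or 4.2 points, and four move it by up to 16.7. The change should be made before patients start to leave.

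**What to change.** Reconcile Section 3.3.2, the text under Table 5, Section 3.6.2, Table 12 footnote j, and the Sample Size and Power and Statistical Analyses text of Section 7.0, so that stopping treatment and leaving the study are separate events. The clinical stopping criteria themselves need not change for this purpose; which time limit applies where Section 3.3.2 and Table 5 differ is for the sponsor to settle.

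Then state that:
- patients who stop drug for toxicity continue disease assessment and survival follow-up, and non-pCR patients among them are counted in the primary analysis;
- the schedule in Section 4.3 includes disease assessment and survival contact after end of treatment, consistent with the follow-up that the sample size assumes;
- RFS follow-up is censored only at withdrawal of consent, loss to follow-up or data cutoff;
- a sensitivity analysis counts patients lost before 12 months first all as relapsed and then all as relapse-free.

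The cost is protocol wording plus scans and contacts for a few patients who stop for toxicity. Adding follow-up after end of treatment to the schedule applies to all patients, but the sample-size assumption already relies on it.

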## **3.7 MANAGEMENT OF IRAES**

Management of spartaLizumab induced immune mediated adverse events should be as per the guidance documents in Appendix B.

If a patient does experience an irAE and prednisone is administered, reduce prednisone dose by 2.5 to 10.0 mg decrements every 3–7 days until physiologic dose (5 to 7.5 mg of prednisone per day) is reached. Consider to complete tapering over a period of at least 4 weeks. Slower tapering of corticosteroids therapy may be recommended if the adverse event is not showing improvement.

Once corticosteroid tapering is achieved at a level of 10 mg of prednisone/day (or equivalent) spartaLizumab can be restarted.

## **3.8 CONCOMITANT AND EXCLUDED THERAPIES**

The following medications or non-drug therapies are prohibited while on treatment in this study:

- Other anti-cancer therapies

### **3.8.1 Other investigational drugs**

The investigator must be informed as soon as possible about any medication taken from the time of screening until 30 days after the last dose of study treatment. Any concomitant medication(s), including dietary supplements, taken during the study will be recorded. The minimum requirement is that drug name, dose, and the dates of administration are to be recorded. ConMeds will be recorded in both EMR and CRF.

Subjects should receive full supportive care during the study, including transfusions of blood and blood products, and treatment with antibiotics, anti-emetics, anti-diarrheals, and analgesics, and other care as deemed appropriate, and in accordance with their institutional guidelines.

